14.7.2.3. Missing Data for Statistical Analysis

Element	Reporting Detail
General	
 • The study is designed to collect data for the 52 weeks following randomisation for all participants, including for participants who prematurely withdraw from interventional product. The following scenarios may arise. 
 1) Participant completes interventional product and study 2) Participant prematurely withdrawn from interventional product and agrees to continued data collection off-treatment for 52 weeks following randomisation 3) Participant prematurely withdrawn from interventional product and initially agrees to continued off-treatment data collection, but subsequently withdraws from the study prior to 52 weeks following randomisation 4) Participant prematurely withdrawn from interventional product and does not agree to continued off-treatment data collection • For participants under any scenario missing data may arise intermittently due to nonattendance at scheduled visits. For participants under scenarios 3 and 4 missing data will arise due to premature withdrawal from the study. • Unless otherwise specified on-treatment data and where available off-treatment data will be included in the analysis of efficacy endpoints.

14.8. Appendix 8: Values of Potential Clinical Importance

14.8.1. Laboratory Values of Potential Clinical Concern

Haematology				
Laboratory Parameter	Units	Age Category (years)	Clinical Concern Range	
			Low Flag (< x)	High Flag (>x)
Hematocrit	Ratio of 1	12+	0.201	0.599
Haemoglobin	G/L	12+	71	199
Platelet Count	GI/L	1+	31	1499
While Blood Cell Count (WBC)	GI/L	12+	1.1	

Clinical Chemistry				
Laboratory Parameter	Units	Age Category (years)	Clinical Concern Range	
			Low Flag (< x)	High Flag (>x)
ALT	U/L	3-12		>143
	U/L	13+		>239
Calcium	mmol/L	3+	1.50	3.24
Creatinine Phosphokinase	IU/L	12+		>5 x ULN
Glucose	mmol/L	1+	2.2	27.8
Phosphorus, Inorg	mmol/L	3+	0.32	
Potassium	mmol/L	3+	2.8	6.5
Sodium	mmol/L	0+	120	160

Possible Hy's Law Cases				
Test Analyte	Units	Category	Clinical Concern Range	
ALT, Bilirubin			ALT \geq 3xULN and Bilirubin \geq 2xULN (>35% direct)	
ALT, INR			ALT \geq 3xULN and INR > 1.5	

NOTES: ULN=Upper Limit of Normal

14.9. Appendix 9: Population Pharmacokinetic (PopPK) Analyses

14.9.1. Population Pharmacokinetic (PopPK) Dataset Specification

Specifications for the generation of the dataset will be provided in a separate document.

14.9.2. Population Pharmacokinetic (PopPK) Methodology

Mepolizumab plasma concentration-time data (samples collected at Weeks 4, 52 and 68; at the Early Withdrawal Visit and the additional follow-up visits (if applicable)) will be analysed by population methods using nonlinear mixed-effects modelling. The analysis will be carried out using appropriate software (e.g., NONMEM or SAS).

14.9.2.1. Base Model

In consideration of the sparse sampling (3 samples post-start of treatment over 68 weeks: Week 4, 52 and 68) and the wealth of mepolizumab PK knowledge, the most recent population PK model will be applied directly to the dataset without estimation (e.g. $\text{maxevals}=0$ in NONMEM) and predictions generated, against which the model will be validated prospectively using appropriate goodness of fit tests. For example, the Anderson-Darling and Cramér-von Mises tests are accepted methods of comparing Empirical Distribution Functions for model and data (i.e. PK concentrations) to evaluate whether independent observations (i.e. observed PK concentrations from the study) are adequately described by a model (i.e. most recent population PK model).

The following will be obtained:

- A description of the key models tested during the model development will be provided and tabulated;
- Population mepolizumab plasma PK parameter estimates with 95% CI from the final model will be tabulated. Goodness of fit plots for the final model will be presented;
- Individual post-hoc PK parameter estimates (such as area under the plasma concentration-time curve over the dosing interval $[AUC(0-\tau)]$, $C_{AV} [AUC(0-\tau)/\tau]$) will be summarised descriptively and listed;
- Individual post-hoc predicted plasma concentrations will be summarised descriptively and listed;
- Accumulation ratio estimate will be assessed at Week 52.

The most recent model consists of a two-compartment pharmacokinetic model with first-order absorption and elimination. Bodyweight is incorporated into the model using allometry with fixed physiological allometric exponents of 0.75 and unity for clearance and volumes, respectively. Albumin and creatinine clearance are also included as covariates of mepolizumab clearance on physiological grounds, however their effects are small and not of clinical relevance. Details of the model can be found in report GlaxoSmithKline Document Number [2015N238436_00](#).

14.9.2.2. Investigation of Covariates

The impact of the following prospectively selected covariates on mepolizumab exposure (e.g. clearance) will be evaluated using the procedures described in Section 14.9.2.3.

Category	Covariates
Demographics	Weight (included in the structural model), age, race, gender, country
Baseline clinical status	Creatinine clearance, albumin (both already included in the current model), serum creatinine, alanine aminotransferase, aspartate aminotransferase, alkaline phosphatase, bilirubin, total protein
Baseline disease status	Total endoscopic NP score (centrally read), mean nasal obstruction VAS, number of previous surgeries, blood eosinophils and baseline OCS dose
Concomitant medications	If data permits ^[1] , e.g. leukotriene receptor antagonists, proton pump inhibitors, statins, antihistamines, pain relief (e.g. paracetamol, NSAIDs) and antihypertensive drugs
Others	Presence/absence of anti-drug antibodies and previous biologics use (monoclonal antibodies).

[1] Attempt to investigate those classes of drug will be made providing data permits.

Covariate selection will be based on physiological plausibility, supported by graphical evaluation (PK parameters vs. covariates), and formally by automated linear model fitting using proc glmselect in SAS 9.4 (or higher). Individual PK parameters and covariates will be log-transformed and standardized before analysis. For forward and backward selections, significance levels of 0.1 and 0.05 will be applied respectively, in line with criteria used in previous analyses. Co-linearity between covariates will be carefully considered.

Identified covariates will then be subjected to traditional covariate analysis (with estimation step) and will follow the procedures described in Section 14.9.2.3. If deemed appropriate box plots of systemic clearance versus covariates of interest (e.g. immunogenicity status) will be provided.

14.9.2.3. Covariate Model Selection Procedures

The covariate model building will follow a step-wise process consisting of a forward and backward selection procedure. The likelihood ratio test will be used to evaluate the significance of incorporating or removing covariates into the population model based on alpha levels set *a priori*. For forward and backward selections, a significance level of 0.05 and 0.01 for first order conditional estimation with interaction (FOCE-I) will be used, respectively, in line with criteria used in previous analyses.

- **Step-wise forward addition procedure**

Each covariate will be included individually in the ‘base model’ to identify covariates resulting in a decrease in the objective function value (OFV) of > 3.84 , $\chi^2 < 0.05$ for 1

degree of freedom (*df*) using FOCE-I. The retained covariates will then be added to the base model one by one, starting with the most significant ones until all covariates have been tested. Note, if a covariate exponent estimate is numerically small, the covariate will not be retained; irrespective of objective function. This will also be supported by examination of the goodness of fit. This will constitute the full model.

- **Backward elimination procedure**

From the full model, the significance of each covariate will be tested individually by removing covariates one by one until all non-significant covariates have been excluded. A covariate will be retained if upon removal, the OFV increase by more than 6.64 points ($\chi^2 < 0.01$ for 1 *df*) using FOCE-I. Note, a covariate may be retained in the model despite being found non-statistically significant, if there is a strong rationale for its inclusion. This will constitute the final model.

Note: centering of continuous covariates may be considered, as appropriate. The mean or median value of the subjects included in the analysis may be used for example.

The impact of the presence of anti-mepolizumab antibodies may not be formally tested as a covariate in the model, considering the low incidence observed in the mepolizumab programme to date. Instead a graphical approach will be used, if deemed appropriate.

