5.4.2. Examination of Subgroups

This section details the subgroups of interest within this study. For each co-primary endpoint, a separate exploratory analysis within each of the subgroup categories will be carried out. Subgroup analyses for all other endpoints are detailed in the statistical methods/analysis sections. Unless otherwise stated no formal hypothesis testing in subgroups of the population will be performed.

Subgroup	Categories
Participants with Asthma	Concurrent asthma, No concurrent asthma
Aspirin Exacerbated Respiratory Disease (AERDS)	Current AERDS, No Current AERDS
Number of previous surgeries	1, 2, >2
Baseline Blood Eosinophil Categories (GI/L)	≤0.3 GI/L; >0.3 to ≤0.5 GI/L; >0.5 to ≤0.7 GI/L; >0.7 GI/L
Region	Europe, United States, Rest of World
Age	18-<40, 40-<65, ≥65 years
Gender	Male, Female
Race	African American/African Heritage, White, Asian, Other

If, following unblinding, the analysis model within a subgroup category fails to converge due to small numbers of participants, the model will be rerun with consideration of further refining regions or if required exclusion of the region covariate. Failing this, subgroup categories may be further refined when possible, otherwise only a descriptive summary of the data will be presented. Footnotes will clearly identify the covariates included in the analysis model.

There is a biological rationale for potentially observing greater efficacy with increasing levels of baseline blood eosinophils. Except for baseline blood eosinophils, differential treatment effects are not expected for any of the other subgroups listed above and therefore any differences in efficacy of mepolizumab compared to placebo observed in subgroup categories will be viewed as exploratory.

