14.10.4. Investigation of Covariates

The impact of the following prospectively selected plausible covariates on relevant parameters (i.e., baseline blood eosinophil count and maximum effect) will be evaluated.

Category	Covariates
Demographics	Age, race, gender
Baseline disease status	Total endoscopic NP score (centrally read), mean nasal obstruction VAS, number of previous surgeries, blood eosinophils and baseline OCS dose
Others	If data permits ^[1] , e.g. leukotriene receptor antagonists,

	proton pump inhibitors, statins, antihistamines, pain relief (e.g. paracetamol, NSAIDs) and antihypertensive drugs
--	--------------------------------------------------------------------------------------------------------------------

[1] Attempt to investigate those covariates will be made providing data permits.

Covariate selection will be based on physiological plausibility, supported by graphical evaluation (PD parameters vs. covariates), and formally by automated linear model fitting using proc glmselect in SAS 9.4 (or higher). Individual PD parameters and covariates will be log-transformed and standardized before analysis. For forward and backward selections, significance levels of 0.1 and 0.05 will be applied respectively, in line with criteria used in previous analyses. Co-linearity between covariates will be carefully considered.

Identified covariates will then be subjected to traditional covariate analysis (with estimation step) and will follow the same procedures as described in Section 14.9.2.3 for the population PK model.

Model evaluation will be as described in Section 14.9.2.4 for the population PK model.

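### SAP 14.9.2.3 applies 1-df OFV cut-offs (3.84 and 6.64) to every covariate, so the stated 0.05 and 0.01 levels do not hold for race or country if either is coded with more than two levels

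*SAP*

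**What the plan says.** SAP 14.9.2.3 bases covariate selection on likelihood-ratio tests at levels fixed in advance: "For forward and backward selections, a significance level of 0.05 and 0.01 for first order conditional estimation with interaction (FOCE-I) will be used". The two steps then turn those levels into numbers.

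- **Forward.** The step opens with "Each covariate will be included individually in the" base model and looks for covariates "resulting in a decrease in the objective function value (OFV) of > 3.84". The SAP marks this as 0.05 for one degree of freedom.
- **Backward.** "A covariate will be retained if upon removal, the OFV increase by more than 6.64 points". The SAP marks this as 0.01 for one degree of freedom.

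No cut-off is printed for a covariate that brings more than one parameter.

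The demographic candidates for the PK model in SAP 14.9.2.2 are: "Weight (included in the structural model), age, race, gender, country". The PKPD list in 14.10.4 has race but not country, and its covariates "will follow the same procedures as described in Section 14.9.2.3 for the population PK model".

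Both sections place a screen before the likelihood-ratio step: physiological plausibility, graphical review and an automated linear-model selection (glmselect) at 0.1 to enter and 0.05 to stay. SAP 14.9.2.3 also drops effects that are numerically small whatever the OFV says, and allows a non-significant covariate to stay if the rationale is strong.

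The coding of race and country for these models is not stated. SAP 14.9.1 and 14.10.1 leave the dataset specifications to a separate document. Elsewhere the SAP groups race for subgroup analysis as "African American/African Heritage, White, Asian, Other" (5.4.2) and lists 11 countries in three regions (5.3).

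**The concern.** A fixed OFV cut-off gives the stated level only when the covariate adds one parameter. Each further parameter raises the OFV change expected by chance, so a multi-level factor clears 3.84 or 6.64 more easily than its nominal level implies. Followed to the letter, 14.9.2.3 would judge race and country more leniently than age, gender or a laboratory value.

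Both modelling exercises aim to find what explains differences between people in exposure or eosinophil response (SAP 10.2 and 11.1). A chance race or country effect could be reported as such an explanation. In the PK model it could also carry into the individual clearance estimates, and SAP 12.2 computes average concentration (Cav) from those for the exploratory exposure-efficacy analysis.

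**Working it through.** **Inputs.** Levels 0.05 and 0.01 and cut-offs 3.84 and 6.64 (SAP 14.9.2.3); screen levels 0.1 and 0.05 (14.9.2.2); four race groups (5.4.2); countries 5 + 1 + 5 = 11 in three regions (5.3); about 200 participants planned on mepolizumab (2.2).

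**1. The SAP's own figures.** At 1 df the chi-square critical values are 3.841 (0.05) and 6.635 (0.01). The tail areas beyond 3.84 and 6.64 are 0.0500 and 0.0100. The printed cut-offs are right for one parameter.

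**2. Parameters per factor (assumption).** With indicator coding, a factor with k levels adds k − 1 parameters: three regions 2, four race groups 3, 11 countries 10. The raw ancestry categories in 14.6.3 number 1 + 2 + 4 + 3 = 10, giving 9. Two-level coding gives 1.

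**3. Null pass rate of the likelihood-ratio step alone.** This is P(chi-square with df degrees of freedom > cut-off).

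| df | Coding assumed | > 3.84 | > 6.64 | Correct 0.05 / 0.01 cut-offs |
|---|---|---|---|---|
| 1 | two levels | 5.0% | 1.0% | 3.84 / 6.63 |
| 2 | three regions | 14.7% | 3.6% | 5.99 / 9.21 |
| 3 | four race groups | 27.9% | 8.4% | 7.81 / 11.34 |
| 9 | ten ancestry groups | 92.2% | 67.5% | 16.92 / 21.67 |
| 10 | 11 countries | 95.4% | 75.9% | 18.31 / 23.21 |

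**4. Adding the screen.** One null factor was simulated on an individual parameter with n = 200 and 20,000 draws. With C ~ chi-square(k − 1) and R ~ chi-square(n − k), the screen is F = [C/(k − 1)] / [R/(n − k)] and the likelihood-ratio statistic is n·ln(1 + C/R).

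| Levels k | LR > 6.64 alone | 0.05 screen and LR > 6.64 | 0.1 screen and LR > 6.64 |
|---|---|---|---|
| 2 | 1.0% | 1.0% | 1.0% |
| 4 | 8.8% | 4.7% | 8.8% |
| 11 | 77.7% | 4.8% | 9.8% |

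The 0.05 column applies if the factor must survive glmselect's removal level. The 0.1 column is the upper case, where only the entry level binds. The 0.05 critical values at 3 and 10 df (7.81 and 18.31) both exceed 6.64. So in this approximation a factor that passes a whole-factor screen at 0.05 also clears the backward cut-off, and the screen sets the error rate.

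**The case against.** The strongest reply is that the SAP makes the alpha levels the rule and prints 3.84 and 6.64 as their 1-df equivalents, labelled as such. A modeller could supply the right value for a larger factor. This reading is fair, and it makes the repair a clarification. But the 1-df case is the only one written, and it is written for every covariate on lists that name race and country.

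Second, 3 and 10 df are assumptions. The race groups and country list come from the efficacy sections, and the modelling dataset is specified elsewhere. Log-transforming and standardising covariates, and the small-effect rule's mention of an exponent, suit single-parameter terms. This stands as a limit on size: merged or empty levels lower the df, and two-level coding removes the problem. The decision rule itself is still in this SAP. How the small-effect rule would work for a factor with several coefficients is not stated.

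Third, a reader might infer from the first table that a null country effect survives about 76% of the time. The documents do not support that, because only covariates identified by the screen reach the likelihood-ratio step. Nor is it shown that the backward step would never filter these factors in practice. The simulation uses one factor and applies both tests to the same directly simulated parameter. The plan fits a population likelihood to sparse samples, with other covariates present and co-linearity considered.

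It would also be wrong to call this a strict 1% test even for single-parameter covariates, given the small-effect and strong-rationale overrides.

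**Conclusion.** The point holds in a limited form. As written, the cut-offs do not deliver 0.05 and 0.01 for race or country unless those factors are coded with two levels. For the likelihood-ratio step alone the excess runs from modest at 2 df to very large at 10 df.

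For the screened sequence, the approximate null pass rate is about 5%, or 9 to 10% in the upper case, against the stated 1%. This assumes indicator coding, a whole-factor screen and one factor considered alone. Plausibility review and the small-effect rule reduce it further, by an amount the documents do not allow one to calculate.

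The consequence is confined to the PK and PKPD covariate modelling and possibly Cav. Country concerns the PK model only. The PKPD and exposure-efficacy analyses are optional, and no change in clearance or in Cav quartile has been quantified. A reader might infer a threat to the efficacy conclusions. There is none: these models play no part in the co-primary or secondary tests in SAP 5.5.

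**What to change.** In SAP 14.9.2.3, replace the two fixed numbers with the chi-square critical value at 0.05 (forward) or 0.01 (backward), with df equal to the number of parameters added or removed. The values are 3.84/6.63 at 1 df, 5.99/9.21 at 2 df, 7.81/11.34 at 3 df and 18.31/23.21 at 10 df. State how race and country are coded, including any merging of sparse levels. The cross-reference in 14.10.4 carries the rule to the PKPD model.

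This takes a sentence or two and no new data. The price is that weak but real race or country effects are less likely to be retained, which the stated 0.01 level already implies.

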14.9.2.4. Model Evaluation

The uncertainty in the parameter estimates will be assessed (e.g. from the standard error estimates provided by NONMEM or from the 95% CI estimates provided by other appropriate analysis conducted using other software). Furthermore, the model performance will be investigated using a set of goodness of fit plots as well as Visual Predictive Check (VPC) method. Other evaluation methods may be used (e.g. bootstrapping) if deemed appropriate.

14.10. Appendix 10: Pharmacokinetic / Pharmacodynamic Analyses

14.10.1. Pharmacokinetic / Pharmacodynamic Dataset Specification

Specifications for the generation of the dataset will be provided in a separate document.

14.10.2. Pharmacokinetic / Pharmacodynamic Methodology

Mepolizumab blood eosinophil count-time data (samples collected every 4 weeks from Baseline to Week 52, and at Weeks 60, 68 and 76) will be analysed by population methods using nonlinear mixed-effects modelling. The analysis will be carried out using appropriate software (e.g., NONMEM or SAS).

14.10.3. Base Model

The most recent population PKPD model will be applied directly to the dataset without estimation (e.g. maxevals=0 in NONMEM) and predictions generated against which the model will be validated prospectively using appropriate goodness of fit tests as described in Section 14.9.2.1 (using the observed data from the study).

The following will be obtained:

- A description of the key models tested during the model development will be provided and tabulated.
- The population PD parameter estimates with 95% CI from the final model will be tabulated. Goodness of fit plots for the final model will be presented.

The most recent population PKPD model consists of an indirect response model parameterised in term of baseline blood eosinophil count (KRO), rate of elimination of eosinophils in the blood (Kout), concentration resulting in 50% of maximum drug effect (IC₅₀) and maximum effect (Imax). Observed baseline blood eosinophil count is included as covariates of both predicted baseline and mepolizumab inhibitory response; and disease for predicted baseline blood eosinophil count. Details of the model can be found in GlaxoSmithKline Document Number [2015N238436_00](#) and GlaxoSmithKline Document Number [2015N255079_00](#) (extension of the former report).

14.10.4. Investigation of Covariates

The impact of the following prospectively selected plausible covariates on relevant parameters (i.e., baseline blood eosinophil count and maximum effect) will be evaluated.

Category	Covariates
Demographics	Age, race, gender
Baseline disease status	Total endoscopic NP score (centrally read), mean nasal obstruction VAS, number of previous surgeries, blood eosinophils and baseline OCS dose
Others	If data permits ^[1] , e.g. leukotriene receptor antagonists,

	proton pump inhibitors, statins, antihistamines, pain relief (e.g. paracetamol, NSAIDs) and antihypertensive drugs
--	--------------------------------------------------------------------------------------------------------------------

[1] Attempt to investigate those covariates will be made providing data permits.

Covariate selection will be based on physiological plausibility, supported by graphical evaluation (PD parameters vs. covariates), and formally by automated linear model fitting using proc glmselect in SAS 9.4 (or higher). Individual PD parameters and covariates will be log-transformed and standardized before analysis. For forward and backward selections, significance levels of 0.1 and 0.05 will be applied respectively, in line with criteria used in previous analyses. Co-linearity between covariates will be carefully considered.

Identified covariates will then be subjected to traditional covariate analysis (with estimation step) and will follow the same procedures as described in Section 14.9.2.3 for the population PK model.

Model evaluation will be as described in Section 14.9.2.4 for the population PK model.

